9.2. Discussion of Study Design

Liposome bupivacaine is approved for infiltration into a surgical wound. This multicenter, randomized, double-blind, parallel-group study is a comparison of the efficacy and safety of liposome bupivacaine to placebo when administered as a femoral nerve block in subjects undergoing unilateral TKA. The double blind study design is intended to avoid potential bias resulting from subject or Investigator knowledge of the assigned treatment.

Total knee arthroplasty is a frequently performed surgical procedure that causes postsurgical pain of considerable intensity and duration. Standard analgesia following TKA often includes IV and PO opioids postoperatively. Therefore, TKA was selected as an appropriate pain model for investigating a sustained-release formulation of bupivacaine, which has the potential to overcome the limitation reported in previous studies with regard to the duration of the analgesic effect obtained with commercially-available products.

During Part 1, subjects will receive a single dose femoral nerve block with one of three dose levels of liposome bupivacaine (67, 133, or 266 mg). An unblinded dose selection committee will review study data, determine the apparent efficacy and safety of each of the three liposome bupivacaine dose levels tested, and recommend a dose level to be tested during Part 2 of the study. In Part 2 of the study, subjects will receive a single dose injection femoral nerve block with the selected dose of liposome bupivacaine (i.e., 67, 133, or 266 mg) or placebo.

All subjects will receive an opioid (morphine, hydromorphone, and/or oxycodone) and conventional bupivacaine HCl, as needed, to control breakthrough postsurgical pain.

Neurological and cardiac assessments will be conducted to rule out bupivacaine toxicity related to high plasma exposure. Additionally, sensory and motor function assessments will be conducted in order to test for restoration of nerve function.

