15.6.5.3 Proportion of Subjects Able to Walk 20 Meters, Unassisted

The proportion of subjects able to walk 20 meters, unassisted with the optional use of a four-legged walker, at 24 hours, 72 hours, and Day 30 will be summarized for each treatment group, for Part 1 and Part 2 separately and combined. For Part 2, the proportion in each of the liposome bupivacaine group will be compared to the placebo group using a chi-square test.

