7. STATISTICAL METHODS OF ANALYSIS

7.1. General Principles

Descriptive statistics (the number of subjects [n], mean, standard deviation [SD], median, minimum, and maximum) will be used to summarize continuous variables. Means and medians will be presented to one more decimal place than the recorded data. Standard deviations will be presented to two more decimal places than the recorded data. Minimum and maximum values will be presented using the same number of decimal places as the recorded data. Percentages will be presented to one decimal place.

In addition, for PK parameters, geometric means and between-subject coefficient of variations (%CV) will be presented.

Frequency distributions (number [n] and percentage of subjects [%]) will be used to summarize categorical or qualitative variables. In general, the denominator for the percentage calculation will be based upon the total number of subjects in the study population for the treatment groups, unless otherwise specified.

All statistical tests will be performed against a two-sided alternative hypothesis with a significance level of 5% ($\alpha = 0.05$), and all confidence intervals (CIs) calculated will be two-sided 95% CIs. All tests will be declared to be statistically significant if the calculated p-value is ≤ 0.05 unless specified otherwise. Tests for binomial proportions will be conducted (1) using a normal approximation whenever each classification cell for each group to be compared contains expected cell counts of 5 or more subjects, or (2) using an exact method whenever any one classification cell for any one group to be compared contains expected cell counts of fewer than 5 subjects.

All analyses will be performed using SAS[®] Software version 9.2 or later.

Pharmacokinetic parameters will be derived using noncompartmental methods with WinNonlin[®] Professional Version 5.2 or later (Pharsight Corp., Cary, North Carolina).

For the listings, subjects will be listed under their randomized treatment, regardless of actual treatment received. Subjects who are randomized but do not receive study drug will be included in the listings with the treatment group identified as “Liposome bupivacaine xx mg, Not Treated” or “Placebo, Not Treated”, depending on their randomized treatment.

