7.8.4. Other Safety Parameters

Neurological Assessments

The proportion of subjects who are oriented will be summarized by treatment group at each time point, for Part 1 and Part 2 separately and combined. Subjects who were 'not assessable'

will not be included in the calculation of the proportion. The proportion of subjects who have at least one of the neurological events and the proportion of subjects who have each of the neurologic events will be summarized by treatment group, for Part 1 and Part 2 separately and combined.

20-Meter Walk Test

The proportion of subjects able to walk 20 meters, unassisted, with the optional use of a four-legged walker, will be summarized by treatment group for Part 1 and Part 2 separately and combined. For Part 2, the proportion in the liposome bupivacaine group will be compared to placebo using a chi-square test.

Physician's Satisfaction with Return of Sensory/Motor Function

The physician will rate his/her satisfaction with return of sensory/motor function as Extremely dissatisfied, Dissatisfied, Neither satisfied nor dissatisfied, Satisfied, or Extremely satisfied at 72 hours and on Day 30. The categories will be summarized by treatment group at each time point for Part 1 and Part 2 separately and combined. For Part 2, a Wilcoxon Rank Sum test will be used to compare liposome bupivacaine to placebo.

Transfusions

The proportion of subjects who had a transfusion (after study drug administration) will be summarized by treatment group for Part 1 and Part 2 separately and combined. To determine if a subject had a transfusion a review of the concomitant medications will be done. Medications such as Packed Red Blood Cells will indicate that a subject had a transfusion.

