8. SAMPLE SIZE CALCULATIONS

Part 1

The sample size for Part 1 of the study was not based on formal statistical power calculations.

Part 2

A study population of approximately 180 subjects is planned with approximately 90 subjects in each treatment group (liposome bupivacaine and placebo). The sample size was estimated based on the results of a Phase 3 hemorrhoidectomy study of liposome bupivacaine versus placebo where the mean (SD) AUC of the NRS-R pain intensity scores through 72 hours was 141 (101) and 202 (104) for the liposome bupivacaine and placebo groups, respectively.

A two-group t-test with 0.05 two-sided significance level will have >97% power to detect a difference in means of 61, assuming that the common SD is 104, when the sample size in each group is 90.

After the data from Part 1 are evaluated, the sample size for Part 2 may be increased. The evaluation of the data did not indicate that the sample size should be increased.

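### The Part 2 20-meter walk comparison is planned as a chi-square test alone, with no difference or confidence interval to show how large a loss of walking ability has been excluded

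*SAP*

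**What the plan says.** The proportion able to walk 20 meters is a safety endpoint (Protocol 12.6). Protocol 9.2 gives the purpose: "sensory and motor function assessments will be conducted in order to test for restoration of nerve function".

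Protocol 15.6.5.3 says the proportion "at 24 hours, 72 hours, and Day 30 will be summarized for each treatment group", and that in Part 2 the liposome bupivacaine proportion "will be compared to the placebo group using a chi-square test". SAP 7.8.4 repeats this: "For Part 2, the proportion in the liposome bupivacaine group will be compared to placebo using a chi-square test".

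The general rules are in SAP 7.1. "All statistical tests will be performed against a two-sided alternative hypothesis with a significance level of 5" percent, with significance declared at p of 0.05 or below, and "using an exact method whenever any one classification cell for any one group to be compared contains expected cell counts of fewer than 5 subjects". SAP 7.1 also says that any confidence intervals calculated are two-sided 95%, but neither document plans one for the walk test.

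The Table 14.3.4-2 shell has yes and no counts with percentages by arm at the three time points, for Part 2 and for Parts 1 and 2 combined. It has no difference, interval or p-value. The next shell, Table 14.3.5-2 (physician satisfaction), does have a p-value column.

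**The concern.** For a safety proportion, the useful result is an estimate of how much worse the active arm might be. A chi-square p-value says whether the data are compatible with no difference. It does not say which losses they are incompatible with. A non-significant result from about 90 subjects per arm could sit beside a substantial loss of walking, and nothing in the planned table would display that uncertainty.

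The documents themselves give motor function weight. Protocol 13.1.10 requires fall precautions and staff education about nerve-block muscle weakness (it speaks of continuous block, whereas study drug is a single injection). SAP 7.9 includes the walk table among those given to the dose-selection committee. The sample size was set on pain AUC, so the precision available for the walk test was never stated.

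There is also a plain mismatch: the text promises a test whose p-value has no place in the table.

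**Working it through.** **1. The plan's own power figure.** Inputs from SAP 8 and Protocol 15.3: 90 per arm, difference 61, SD 104, two-sided 0.05.

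z = 61 / (104 × √(2/90)) = 61 / 15.50 = 3.93. Power = Φ(3.93 − 1.96) = 97.6% (97.5% by the noncentral t). This agrees with the stated >97%. It is the only power figure in the documents, and it does not concern the walk test. SAP 8 records that the sample size was not increased after Part 1.

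**2. What the chi-square test can miss.** From the documents: 90 per arm and two-sided 0.05. Assumed, because the documents give no walk rates and no loss of interest: a true loss of 15 points and placebo walking rates from 50% to 95%. With p1 for placebo, p2 = p1 − 0.15 and p̄ their mean:

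power = Φ( [0.15 − 1.96 × √(2p̄(1−p̄)/90)] / √([p1(1−p1) + p2(1−p2)]/90) )

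Example, 50% vs 35%: (0.15 − 1.96 × 0.0737) / 0.0728 = 0.076, so power is 53.0% and the miss rate 47.0%.

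| Placebo vs liposome bupivacaine | Miss rate, formula | Miss rate, exact binomial enumeration |
|---|---|---|
| 50% vs 35% | 47.0% | 47.0% |
| 60% vs 45% | 47.8% | 49.4% |
| 70% vs 55% | 45.2% | 44.2% |
| 80% vs 65% | 38.3% | 37.9% |
| 90% vs 75% | 24.1% | 23.3% |
| 95% vs 80% | 13.3% | 11.0% |

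The peak is near 57.5% vs 42.5%: 47.9% by formula, 49.6% exact. These rates are for the uncorrected test at a single time point. With a continuity correction, the range over placebo rates of 50-90% is about 29-55%. With 80 evaluable per arm it is 28-53% (exact, uncorrected). The smallest loss detectable with 80% power at 90 per arm is about 20 points at placebo rates of 50-70%, 19 at 80% and 16 at 90%.

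The small-cell rule hardly matters here: at 95% vs 80% the expected number unable to walk is 90 × 0.125 = 11.25 per arm.

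**3. What a non-significant result can conceal.** Differences are liposome bupivacaine minus placebo, with simple Wald intervals.

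- 32/90 vs 45/90: chi-square = 180 × (45×58 − 45×32)² / (90 × 90 × 77 × 103) = 3.836, below 3.841. Difference −14.4 points, interval −28.7 to −0.1.
- 72/90 vs 81/90: chi-square = 180 × (81×18 − 9×72)² / (90 × 90 × 153 × 27) = 3.53. Difference −10.0 points, interval −20.3 to +0.3.

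In the first case the Wald interval just excludes zero although the test is not significant, because it uses an unpooled variance. A Miettinen-Nurminen interval would include zero: at zero difference its statistic is 3.836 × 179/180 = 3.81, below 3.841. Either way, a loss of well over 20 points is not excluded.

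**4. What an interval would deliver.** With equal true rates p, the half-width is 1.96 × √(2p(1−p)/90): 14.6 points at 50%, 13.4 at 70%, 11.7 at 80% and 8.8 at 90%.

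**The case against.** A reader might infer that p > 0.05 would be taken as restored motor function. The documents do not support that. Protocol 9.2 says why motor function is assessed; it is not a between-arm decision rule. SAP 7.1 defines only when a test is significant. A two-sided test on a safety proportion can also serve as a screen for harm.

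Nor is motor safety judged by this test alone. The table gives the proportions by arm, so the difference, and an approximate interval, can be worked out from it: 50.0% against 35.6% would be visible to anyone. Physician-rated return of sensory and motor function is tested separately (Wilcoxon), and adverse events are tabulated.

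The plan does not hold safety to a visibly lower standard either. Binary efficacy endpoints (pain-free, rescue categories) also get a chi-square p-value without a difference or interval. The intervals on AUC and opioid use belong to continuous measures.

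Finally, the miss rates depend on an assumed loss and assumed placebo rates, and fall to about 11% at 95%. They apply to one time point; a persistent loss is less likely to be missed at all three.

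All of this stands, and it limits the point to reporting. It does not remove it. None of the other planned outputs puts a limit on the loss of walking, leaving readers to derive the interval is a poor substitute for reporting it, and the table still omits the planned p-value.

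**Conclusion.** The point holds as a cheap improvement to analysis and reporting. The only inference planned on the Part 2 walk test is a chi-square test, without the estimate and interval needed to say how large a loss has been excluded, and the table shell does not carry even the p-value.

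The sizes are illustrations. Under an assumed 15-point loss, 90 per arm and one time point, the test misses the loss about 47-50% of the time at placebo walking rates of 50-60%, 38% at 80%, 23% at 90% and 11% at 95%. No single range can be quoted without stating the placebo rate. The points that need no such assumption are that the interval and p-value are absent from the plan and that a p-value cannot bound a loss.

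**What to change.** In SAP 7.8.4, Protocol 15.6.5.3 and Table 14.3.4-2:

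- Report the difference in the proportion able to walk (liposome bupivacaine minus placebo) with a two-sided 95% CI, for example Miettinen-Nurminen or Newcombe, at 24 hours, 72 hours and Day 30 in Part 2.
- Add the planned chi-square p-value to the table as supportive.
- State that the motor-safety conclusion rests on the estimate and its interval, and that non-significance is not evidence of no motor loss.

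No non-inferiority margin is needed: the lower confidence limit shows the largest loss not excluded.

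The cost is a few sentences and some extra columns in one table, with no new data, subjects or procedures. The downside is that the interval will be wide, so the safety statement may have to be more modest. That uncertainty is already in the design, and the present table does not show it.

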7.9. Interim Analysis

After all subjects have completed the 72-hour assessments, or discontinued prior to the 72-hour assessment from Part 1 of the study, an analysis will be conducted in order to select a single therapeutic dose from the three liposome bupivacaine dose levels tested. The committee will determine the apparent efficacy and safety of each of the three liposome bupivacaine dose levels tested and will recommend a dose level for Part 2 of the study. In order to make their assessment, the following tables will be produced by an unblinded statistician:

Table #	Table Title
14.1.1-1	Subject Disposition (All Subjects)
14.1.2.1-1	Demographic and Baseline Characteristics (Safety Analysis Set)
14.2.2.1-1	AUC of NRS-R Pain Intensity Scores Through 72 Hours wWOCF + LOCF Imputation for the Pain Scores (Efficacy Analysis Set)
14.2.2.2-1	Total Postoperative Consumption (mg) of Opioid Rescue Pain Medication Through 72 Hours (Efficacy Analysis Set)
14.2.2.3.2-1	Time to First Opioid Rescue (Efficacy Analysis Set)
14.3.1.2-1	Incidence of Treatment-Emergent Adverse Events (Safety Analysis Set)
14.3.4-1	20-Meter Walk Test (Safety Analysis Set)

In addition, blood plasma samples for PK analysis will be sent to a laboratory for analysis from approximately 100 subjects. The samples from those subjects who received liposome bupivacaine and who did not receive conventional bupivacaine HCl postsurgically will be assayed. The liposome bupivacaine concentrations will be sent to the unblinded statistician. The unblinded statistician will determine the C_{max} for each of these subjects. The maximum C_{max} will be provided to Pacira. Depending on the maximum C_{max} , Pacira will determine if ECG data at T_{max} need to be provided to the committee.

8. SAMPLE SIZE CALCULATIONS

Part 1

The sample size for Part 1 of the study was not based on formal statistical power calculations.

Part 2

A study population of approximately 180 subjects is planned with approximately 90 subjects in each treatment group (liposome bupivacaine and placebo). The sample size was estimated based on the results of a Phase 3 hemorrhoidectomy study of liposome bupivacaine versus placebo where the mean (SD) AUC of the NRS-R pain intensity scores through 72 hours was 141 (101) and 202 (104) for the liposome bupivacaine and placebo groups, respectively.

A two-group t-test with 0.05 two-sided significance level will have >97% power to detect a difference in means of 61, assuming that the common SD is 104, when the sample size in each group is 90.

After the data from Part 1 are evaluated, the sample size for Part 2 may be increased. The evaluation of the data did not indicate that the sample size should be increased.

10. LAYOUT OF TABLES, LISTINGS, AND FIGURES

The following are planned summary tables for Protocol 402-C-323. Tables will be numbered according to the nomenclature used to support the CSR. The final table numbering may be different from the SAP. No amendment will be made for changes in table numbering. All headers, titles, footnotes, and footers specified in the table templates will be displayed in the produced output unless otherwise specified. Notes to programmers will not be included in the tables. There will be a footnote in all tables that includes the program name, SAS version number, and the date that the output was produced.

Study Part 1 Planned Tables

Table Number	Table Title
14.1.1-1	Subject Disposition Study Part 1 (All Randomized Subjects)
14.1.2.1-1	Demographic and Baseline Characteristics Study Part 1 (Safety Analysis Set)
14.1.2.2-1	Demographic and Baseline Characteristics Study Part 1 (Efficacy Analysis Set)
14.1.3.1-1	Prior Medications Study Part 1 (Safety Analysis Set)
14.1.3.2-1	Concomitant Medications Study Part 1 (Safety Analysis Set)
14.2.1.1-1	Study Drug Administration Study Part 1 (Safety Analysis Set)
14.2.1.2-1	Surgery Study Part 1 (Efficacy Analysis Set)
14.2.2.1-1	AUC of NRS-R Pain Intensity Scores Through 72 Hours wWOCF + LOCF Imputation for the Pain Scores Study Part 1 (Efficacy Analysis Set)
14.2.2.2-1	Total Postoperative Consumption (mg) of Opioid Rescue Pain Medication Through 72 Hours Study Part 1 (Efficacy Analysis Set)
14.2.2.3-1	Time to First Opioid Rescue Study Part 1 (Efficacy Analysis Set)

Study Part 1 Planned Tables Continued

Table Number	Table Title
14.2.2.4-1	NRS-R Pain Intensity Scores Study Part 1 (Efficacy Analysis Set)
14.2.2.5-1	NRS-A Pain Intensity Scores Study Part 1 (Efficacy Analysis Set)
14.2.2.6-1	AUC of NRS-R Pain Intensity Scores Through 24, 36, 48, and 60 Hours wWOFCF + LOCF Imputation for the Pain Scores Study Part 1 (Efficacy Analysis Set)
14.2.2.7-1	AUC of NRS-A Pain Intensity Scores Through 24, 36, 48, 60, and 72 Hours wWOFCF + LOCF Imputation for the Pain Scores Study Part 1 (Efficacy Analysis Set)
14.2.2.8-1	AUC of NRS-R Pain Intensity Scores 24-48 and 48-72 Hours wWOFCF + LOCF Imputation for the Pain Scores Study Part 1 (Efficacy Analysis Set)
14.2.2.9-1	Percentage of Subjects who are Pain Free at Each Time Point Study Part 1 (Efficacy Analysis Set)
14.2.2.10-1	Total Postoperative Consumption (mg) of Opioid Rescue Pain Medication Through 24, 36, 48, and 60 Hours Study Part 1 (Efficacy Analysis Set)
14.2.2.11-1	Subjects who Received Rescue Medication Through 72 Hours Study Part 1 (Efficacy Analysis Set)
14.2.2.12-1	Overall Benefit of Analgesia Score Questionnaire (Total Scores) Study Part 1 (Efficacy Analysis Set)
14.2.2.13-1	Subject Satisfaction with Postsurgical Pain Control Study Part 1 (Efficacy Analysis Set)
14.2.2.14-1	Time to Sensitivity to Cold Study Part 1 (Efficacy Analysis Set)

Study Part 1 Planned Tables Continued

Table Number	Table Title
14.2.2.15-1	Incidence of Predefined Treatment-Emergent Opioid-Related Adverse Events Study Part 1 (Efficacy Analysis Set)
14.2.3.1-1	Bupivacaine Plasma Concentrations (ng/mL) Study Part 1 (PK Analysis Set)
14.2.3.2-1	Bupivacaine Plasma Pharmacokinetic Parameters Study Part 1 (PK Analysis Set)
14.2.3.3-1	Percentage of Unbound Bupivacaine Plasma Concentrations (ng/mL) Study Part 1 (PK Analysis Set)
14.3.1.1-1	Overview of Treatment-Emergent Adverse Events Study Part 1 (Safety Analysis Set)
14.3.1.2-1	Incidence of Treatment-Emergent Adverse Events Study Part 1 (Safety Analysis Set)
14.3.1.3-1	Incidence of Study Drug Related Treatment-Emergent Adverse Events Study Part 1 (Safety Analysis Set)
14.3.1.4-1	Incidence of Treatment-Emergent Adverse Events by Severity (Part 1 of 2) Study Part 1 (Safety Analysis Set)
14.3.1.4-1	Incidence of Treatment-Emergent Adverse Events by Severity (Part 2 of 2) Study Part 1 (Safety Analysis Set)
14.3.1.5-1	Incidence of Serious Treatment-Emergent Adverse Events Study Part 1 (Safety Analysis Set)
14.3.2.1-1	Vital Signs Study Part 1 (Safety Analysis Set)
14.3.2.2-1	Vital Signs Change from Baseline Study Part 1 (Safety Analysis Set)
14.3.3-1	Neurological Assessment Study Part 1 (Safety Analysis Set)

Study Part 1 Planned Tables Continued

Table Number	Table Title
14.3.4-1	20-Meter Walk Test Study Part 1 (Safety Analysis Set)
14.3.5-1	Physician Satisfaction with Return of Sensory/Motor Function Study Part 1 (Safety Analysis Set)
14.3.6-1	Incidence of Transfusions Study Part 1 (Safety Analysis Set)

Study Part 1 Planned Figure

Figure Number	Table Title
1-1	Sensitivity to Cold Study Part 1 (Efficacy Analysis Set)

Study Part 2 Planned Tables

Table Number	Table Title
14.1.1.1-2	Subject Disposition Study Part 2 (All Randomized Subjects)
14.1.1.2-2	Subject Disposition by Site Study Part 2 (All Randomized Subjects)
14.1.2.1-2	Demographic and Baseline Characteristics Study Part 2 (Safety Analysis Set)
14.1.2.2-2	Demographic and Baseline Characteristics Study Part 2 (Efficacy Analysis Set)
14.1.3.1-2	Prior Medications Study Part 2 (Safety Analysis Set)
14.1.3.2-2	Concomitant Medications Study Part 2 (Safety Analysis Set)
14.2.1.1-2	Study Drug Administration Study Part 2 (Safety Analysis Set)
14.2.1.2-2	Surgery Study Part 2 (Efficacy Analysis Set)
14.2.2.1.1-2	AUC of NRS-R Pain Intensity Scores Through 72 Hours wWOCF + LOCF Imputation for the Pain Scores Study Part 2 (Efficacy Analysis Set)
14.2.2.1.2-2	AUC of NRS-R Pain Intensity Scores Through 72 Hours by Site wWOCF + LOCF Imputation for the Pain Scores Study Part 2 (Efficacy Analysis Set)

Study Part 2 Planned Tables Continued

Table Number	Table Title
14.2.2.1.3-2	AUC of NRS-R Pain Intensity Scores Through 72 Hours wWOCF + LOCF Imputation for the Pain Scores Excluding Subjects with PCA Interval Data Study Part 2 (Efficacy Analysis Set)
14.2.2.2-2	Total Postoperative Consumption (mg) of Opioid Rescue Pain Medication Through 72 Hours Study Part 2 (Efficacy Analysis Set)
14.2.2.3.2-2	Time to First Opioid Rescue Study Part 2 (Efficacy Analysis Set)
14.2.2.4-2	NRS-R Pain Intensity Scores Study Part 2 (Efficacy Analysis Set)
14.2.2.5-2	NRS-A Pain Intensity Scores Study Part 2 (Efficacy Analysis Set)
14.2.2.6-2	AUC of NRS-R Pain Intensity Scores Through 24, 36, 48, and 60 Hours wWOCF + LOCF Imputation for the Pain Scores Study Part 2 (Efficacy Analysis Set)
14.2.2.7-2	AUC of NRS-A Pain Intensity Scores Through 24, 36, 48, 60, and 72 Hours wWOCF + LOCF Imputation for the Pain Scores Study Part 2 (Efficacy Analysis Set)
14.2.2.8-2	AUC of NRS-R Pain Intensity Scores 24-48 and 48-72 Hours wWOCF + LOCF Imputation for the Pain Scores Study Part 2 (Efficacy Analysis Set)
14.2.2.9-2	Percentage of Subjects who are Pain Free at Each Time Point Study Part 2 (Efficacy Analysis Set)
14.2.2.10-2	Total Postoperative Consumption (mg) of Opioid Rescue Pain Medication Through 24, 36, 48, and 60 Hours Study Part 2 (Efficacy Analysis Set)

Study Part 2 Planned Tables Continued

Table Number	Table Title
14.2.2.11-2	Subjects who Received Rescue Medication Through 72 Hours Study Part 2 (Efficacy Analysis Set)
14.2.2.12-2	Overall Benefit of Analgesia Score Questionnaire (Total Scores) Study Part 2 (Efficacy Analysis Set)
14.2.2.13-2	Subject Satisfaction with Postsurgical Pain Control Study Part 2 (Efficacy Analysis Set)
14.2.2.14-2	Time to Sensitivity to Cold Study Part 2 (Efficacy Analysis Set)
14.3.1.1-2	Overview of Treatment-Emergent Adverse Events Study Part 2 (Safety Analysis Set)
14.3.1.2-2	Incidence of Treatment-Emergent Adverse Events Study Part 2 (Safety Analysis Set)
14.3.1.3-2	Incidence of Study Drug Related Treatment-Emergent Adverse Events Study Part 2 (Safety Analysis Set)
14.3.1.4-2	Incidence of Treatment-Emergent Adverse Events by Severity (Part 1 of 2) Study Part 2 (Safety Analysis Set)
14.3.1.4-2	Incidence of Treatment-Emergent Adverse Events by Severity (Part 2 of 2) Study Part 2 (Safety Analysis Set)
14.3.1.5-2	Incidence of Serious Treatment-Emergent Adverse Events Study Part 2 (Safety Analysis Set)
14.3.2.1-2	Vital Signs Study Part 2 (Safety Analysis Set)

Study Part 2 Planned Tables Continued

Table Number	Table Title
14.3.2.2-2	Vital Signs Change from Baseline Study Part 2 (Safety Analysis Set)
14.3.3-2	Neurological Assessment Study Part 2 (Safety Analysis Set)
14.3.4-2	20-Meter Walk Test Study Part 2 (Safety Analysis Set)
14.3.5-2	Physician Satisfaction with Return of Sensory/Motor Function Study Part 2 (Safety Analysis Set)
14.3.6-2	Incidence of Transfusions Study Part 2 (Safety Analysis Set)

Study Part 2 Planned Figure

Figure Number	Table Title
1-2	Sensitivity to Cold Study Part 2 (Efficacy Analysis Set)

Planned Listings

Listing Number	Listing Title
16.1.1	Eligibility
16.1.2	Unblinding
16.1.3	Subject Populations and Discontinuations
16.1.4	Hospital Discharge
16.2	Demographics
16.3.1	Medical History
16.3.2	Physical Examination
16.3.3	Electrocardiogram Recording (Holter Monitoring)
16.3.4	Prior and Concomitant Medications (Except for Rescue Pain Medications)
16.3.5	Transfusions Post Study Drug Administration
16.4.1	Study Drug Exposure
16.4.2	Surgery
16.5.1.1	Pain Intensity Scores at Rest and with Activity
16.5.1.2	AUC of NRS-R and NRS-A Pain Intensity Scores wWOCF + LOCF Imputation for the Pain Scores
16.5.2.1	Postoperative Consumption of Opioid Rescue Pain Medication
16.5.2.2	Postoperative Consumption of Rescue Pain Medication via PCA Pump (Interval Data)
16.5.2.3	Postoperative Consumption of Conventional Bupivacaine HCl Rescue Pain Medication
16.5.3	Overall Benefit of Analgesia Score Questionnaire
16.5.4	Subject Satisfaction with Postsurgical Pain Control
16.5.5	Sensitivity to Cold
16.5.6	Predefined Treatment-Emergent Opioid-Related Adverse Events at 72 Hours (Study Part 1)
16.6.1	Scheduled Bupivacaine Plasma Concentrations (Study Part 1)
16.6.2	Bupivacaine Plasma Pharmacokinetic Parameters (Study Part 1)
16.6.3	Unscheduled Bupivacaine Plasma Concentrations
16.7.1.1	Adverse Events (Part 1 of 2)
16.7.1.2	Adverse Events (Part 2 of 2)
16.7.1.3	Serious Adverse Events (Part 1 of 2)
16.7.1.4	Serious Adverse Events (Part 2 of 2)
16.7.1.5	Deaths
16.8	Height, Weight, and Vital Signs
16.9	Neurological Assessment
16.10	20-Meter Walk Test
16.11	Physician Satisfaction with Return of Sensory/Motor Function

STUDY PART 1 TABLES

Pacira Pharmaceuticals, Inc.
402-C-323

Table 14.1.1-1 (Page x of Y)
Subject Disposition
Study Part 1
(All Randomized Subjects)

	LB 67 mg (N=XX) n (%)	LB 133 mg (N=XX) n (%)	LB 266 mg (N=XX) n (%)	Placebo (N=XX) n (%)	All Subjects (N=XX) n (%)
Safety Analysis Set [1]	00 (00.0)	00 (00.0)	00 (00.0)	00 (00.0)	00 (00.0)
Efficacy Analysis Set [2]	00 (00.0)	00 (00.0)	00 (00.0)	00 (00.0)	00 (00.0)
PK Analysis Set [3]	00 (00.0)	00 (00.0)	00 (00.0)	NA	00 (00.0)
Subjects Who Completed the Study	00 (00.0)	00 (00.0)	00 (00.0)	00 (00.0)	00 (00.0)
Subjects Who Terminated Early	00 (00.0)	00 (00.0)	00 (00.0)	00 (00.0)	00 (00.0)
Reason for Early Termination					
Subject Death	00 (00.0)	00 (00.0)	00 (00.0)	00 (00.0)	00 (00.0)
Adverse Event	00 (00.0)	00 (00.0)	00 (00.0)	00 (00.0)	00 (00.0)
Lack of Efficacy	00 (00.0)	00 (00.0)	00 (00.0)	00 (00.0)	00 (00.0)
Lost to Follow-up	00 (00.0)	00 (00.0)	00 (00.0)	00 (00.0)	00 (00.0)
Withdrawal by Subject	00 (00.0)	00 (00.0)	00 (00.0)	00 (00.0)	00 (00.0)
Other	00 (00.0)	00 (00.0)	00 (00.0)	00 (00.0)	00 (00.0)

LB = liposome bupivacaine.

[1] The safety analysis set includes all subjects who received study drug.

[2] The efficacy analysis set includes all subjects in the safety analysis set who underwent the planned surgery.

[3] The PK analysis set includes all subjects in the safety analysis set who received liposome bupivacaine, provided sufficient samples to allow for calculation of PK parameters required for analysis, and who did not receive conventional bupivacaine HCl postsurgically.

Reference: [Listing 16.1.3](#).

Pacira Pharmaceuticals, Inc.
402-C-323

Table 14.1.2.1-1 (Page x of Y)
Demographic and Baseline Characteristics
Study Part 1
(Safety Analysis Set)

	LB 67 mg (N=XX)	LB 133 mg (N=XX)	LB 266 mg (N=XX)	Placebo (N=XX)	All Subjects (N=XX)
Age (years)					
n	00	00	00	00	00
Mean	00.0	00.0	00.0	00.0	00.0
SD	00.00	00.00	00.00	00.00	00.00
Median	00	00	00	00	00
Minimum, Maximum	00, 00	00, 00	00, 00	00, 00	00, 00
Age Category					
<65	00 (00.0)	00 (00.0)	00 (00.0)	00 (00.0)	00 (00.0)
>=65	00 (00.0)	00 (00.0)	00 (00.0)	00 (00.0)	00 (00.0)
Gender					
Male	00 (00.0)	00 (00.0)	00 (00.0)	00 (00.0)	00 (00.0)
Female	00 (00.0)	00 (00.0)	00 (00.0)	00 (00.0)	00 (00.0)
Ethnic Group					
Hispanic or Latino	00 (00.0)	00 (00.0)	00 (00.0)	00 (00.0)	00 (00.0)
Not Hispanic or Latino	00 (00.0)	00 (00.0)	00 (00.0)	00 (00.0)	00 (00.0)
Race [1]					
American Indian/Alaskan Native	00 (00.0)	00 (00.0)	00 (00.0)	00 (00.0)	00 (00.0)
Asian	00 (00.0)	00 (00.0)	00 (00.0)	00 (00.0)	00 (00.0)
Black or African American	00 (00.0)	00 (00.0)	00 (00.0)	00 (00.0)	00 (00.0)
Native Hawaiian/Other Pacific Islander	00 (00.0)	00 (00.0)	00 (00.0)	00 (00.0)	00 (00.0)
White	00 (00.0)	00 (00.0)	00 (00.0)	00 (00.0)	00 (00.0)
Other	00 (00.0)	00 (00.0)	00 (00.0)	00 (00.0)	00 (00.0)

LB = liposome bupivacaine.

[1] Subjects may be counted in more than one category.

Reference: [Listings 16.2](#) and [16.8](#).

Pacira Pharmaceuticals, Inc.
402-C-323

Table 14.1.2.1-1 (Page x of Y)
Demographic and Baseline Characteristics
Study Part 1
(Safety Analysis Set)

	LB 67 mg (N=XX)	LB 133 mg (N=XX)	LB 266 mg (N=XX)	Placebo (N=XX)	All Subjects (N=XX)
ASA Class					
1	00 (00.0)	00 (00.0)	00 (00.0)	00 (00.0)	00 (00.0)
2	00 (00.0)	00 (00.0)	00 (00.0)	00 (00.0)	00 (00.0)
3	00 (00.0)	00 (00.0)	00 (00.0)	00 (00.0)	00 (00.0)
Height (cm)					
n	00	00	00	00	00
Mean	00.0	00.0	00.0	00.0	00.0
SD	00.00	00.00	00.00	00.00	00.00
Median	00	00	00	00	00
Minimum, Maximum	00, 00	00, 00	00, 00	00, 00	00, 00
Weight (kg)					
n	00	00	00	00	00
Mean	00.0	00.0	00.0	00.0	00.0
SD	00.00	00.00	00.00	00.00	00.00
Median	00	00	00	00	00
Minimum, Maximum	00, 00	00, 00	00, 00	00, 00	00, 00

ASA = American Society of Anesthesiologists; LB = liposome bupivacaine.

[1] Subjects may be counted in more than one category.

Reference: [Listings 16.2](#) and [16.8](#).

Pacira Pharmaceuticals, Inc.
402-C-323

Table 14.1.2.2-1 (Page x of Y)
Demographic and Baseline Characteristics
Study Part 1
(Efficacy Analysis Set)

	LB 67 mg (N=XX)	LB 133 mg (N=XX)	LB 266 mg (N=XX)	Placebo (N=XX)	All Subjects (N=XX)
Age (years)					
n	00	00	00	00	00
Mean	00.0	00.0	00.0	00.0	00.0
SD	00.00	00.00	00.00	00.00	00.00
Median	00	00	00	00	00
Minimum, Maximum	00, 00	00, 00	00, 00	00, 00	00, 00
Age Category					
<65	00 (00.0)	00 (00.0)	00 (00.0)	00 (00.0)	00 (00.0)
>=65	00 (00.0)	00 (00.0)	00 (00.0)	00 (00.0)	00 (00.0)
Gender					
Male	00 (00.0)	00 (00.0)	00 (00.0)	00 (00.0)	00 (00.0)
Female	00 (00.0)	00 (00.0)	00 (00.0)	00 (00.0)	00 (00.0)
Ethnic Group					
Hispanic or Latino	00 (00.0)	00 (00.0)	00 (00.0)	00 (00.0)	00 (00.0)
Not Hispanic or Latino	00 (00.0)	00 (00.0)	00 (00.0)	00 (00.0)	00 (00.0)
Race [1]					
American Indian/Alaskan Native	00 (00.0)	00 (00.0)	00 (00.0)	00 (00.0)	00 (00.0)
Asian	00 (00.0)	00 (00.0)	00 (00.0)	00 (00.0)	00 (00.0)
Black or African American	00 (00.0)	00 (00.0)	00 (00.0)	00 (00.0)	00 (00.0)
Native Hawaiian/Other Pacific Islander	00 (00.0)	00 (00.0)	00 (00.0)	00 (00.0)	00 (00.0)
White	00 (00.0)	00 (00.0)	00 (00.0)	00 (00.0)	00 (00.0)
Other	00 (00.0)	00 (00.0)	00 (00.0)	00 (00.0)	00 (00.0)

LB = liposome bupivacaine.

[1] Subjects may be counted in more than one category.

Reference: [Listings 16.2](#) and [16.8](#).

Pacira Pharmaceuticals, Inc.
402-C-323

Table 14.1.2.2-1 (Page x of Y)
Demographic and Baseline Characteristics
Study Part 1
(Efficacy Analysis Set)

	LB 67 mg (N=XX)	LB 133 mg (N=XX)	LB 266 mg (N=XX)	Placebo (N=XX)	All Subjects (N=XX)
ASA Class					
1	00 (00.0)	00 (00.0)	00 (00.0)	00 (00.0)	00 (00.0)
2	00 (00.0)	00 (00.0)	00 (00.0)	00 (00.0)	00 (00.0)
3	00 (00.0)	00 (00.0)	00 (00.0)	00 (00.0)	00 (00.0)
Height (cm)					
n	00	00	00	00	00
Mean	00.0	00.0	00.0	00.0	00.0
SD	00.00	00.00	00.00	00.00	00.00
Median	00	00	00	00	00
Minimum, Maximum	00, 00	00, 00	00, 00	00, 00	00, 00
Weight (kg)					
n	00	00	00	00	00
Mean	00.0	00.0	00.0	00.0	00.0
SD	00.00	00.00	00.00	00.00	00.00
Median	00	00	00	00	00
Minimum, Maximum	00, 00	00, 00	00, 00	00, 00	00, 00

ASA = American Society of Anesthesiologists; LB = liposome bupivacaine.

[1] Subjects may be counted in more than one category.

Reference: [Listings 16.2](#) and [16.8](#).

Pacira Pharmaceuticals, Inc.
402-C-323

Table 14.1.3.1-1 (Page x of Y)
Prior Medications
Study Part I
(Safety Analysis Set)

ATC Class WHO-DD Preferred Term	LB 67 mg (N=XX) n (%)	LB 133 mg (N=XX) n (%)	LB 266 mg (N=XX) n (%)	Placebo (N=XX) n (%)	All Subjects (N=XX) n (%)
Any Prior Medication	00 (00.0)	00 (00.0)	00 (00.0)	00 (00.0)	00 (00.0)
ATC Class 1	00 (00.0)	00 (00.0)	00 (00.0)	00 (00.0)	00 (00.0)
Preferred Term 1	00 (00.0)	00 (00.0)	00 (00.0)	00 (00.0)	00 (00.0)
Preferred Term 2	00 (00.0)	00 (00.0)	00 (00.0)	00 (00.0)	00 (00.0)
....					
ATC Class 2	00 (00.0)	00 (00.0)	00 (00.0)	00 (00.0)	00 (00.0)
Preferred Term 3	00 (00.0)	00 (00.0)	00 (00.0)	00 (00.0)	00 (00.0)
Preferred Term 4	00 (00.0)	00 (00.0)	00 (00.0)	00 (00.0)	00 (00.0)

ATC = Anatomical Therapeutic Chemical classification system; LB = liposome bupivacaine; WHO-DD = World Health Organization Drug Dictionary.

Note: Prior medications are defined as medication with a stop date/time prior to study drug administration.

At each level of summation (overall, ATC class, and preferred term), subjects are only counted once.

Reference: [Listing 16.3.4](#).

Pacira Pharmaceuticals, Inc.
402-C-323

Table 14.1.3.2-1 (Page x of Y)
Concomitant Medications
Study Part 1
(Safety Analysis Set)

ATC Class WHO-DD Preferred Term	LB 67 mg (N=XX)	LB 133 mg (N=XX)	LB 266 mg (N=XX)	Placebo (N=XX)	All Subjects (N=XX)
	n (%)	n (%)	n (%)	n (%)	n (%)
Any Prior Medication	00 (00.0)	00 (00.0)	00 (00.0)	00 (00.0)	00 (00.0)
ATC Class 1	00 (00.0)	00 (00.0)	00 (00.0)	00 (00.0)	00 (00.0)
Preferred Term 1	00 (00.0)	00 (00.0)	00 (00.0)	00 (00.0)	00 (00.0)
Preferred Term 2	00 (00.0)	00 (00.0)	00 (00.0)	00 (00.0)	00 (00.0)
....					
ATC Class 2	00 (00.0)	00 (00.0)	00 (00.0)	00 (00.0)	00 (00.0)
Preferred Term 3	00 (00.0)	00 (00.0)	00 (00.0)	00 (00.0)	00 (00.0)
Preferred Term 4	00 (00.0)	00 (00.0)	00 (00.0)	00 (00.0)	00 (00.0)

ATC = Anatomical Therapeutic Chemical classification system; LB = liposome bupivacaine; WHO-DD = World Health Organization Drug Dictionary.

Note: Concomitant medications are defined as medications (other than rescue pain medication) taken on or after the start of study drug administration. This table does not include rescue pain medications.

At each level of summation (overall, ATC class, and preferred term), subjects are only counted once.

Reference: [Listing 16.3.4.1](#).

Pacira Pharmaceuticals, Inc.
402-C-323

Table 14.2.1.1-1 (Page x of Y)
Study Drug Administration
Study Part 1
(Safety Analysis Set)

	LB 67 mg (N=XX)	LB 133 mg (N=XX)	LB 266 mg (N=XX)	Placebo (N=XX)
Duration of Injection (min)				
n	00	00	00	00
Mean	00.0	00.0	00.0	00.0
SD	00.00	00.00	00.00	00.00
Median	00	00	00	00
Minimum, Maximum	00, 00	00, 00	00, 00	00, 00
Volume of Study Drug Administered (mL)				
n	00	00	00	00
Mean	00.0	00.0	00.0	00.0
SD	00.00	00.00	00.00	00.00
Median	00	00	00	00
Minimum, Maximum	00, 00	00, 00	00, 00	00, 00

LB = liposome bupivacaine.

Reference: [Listing 16.4.1.](#)

Pacira Pharmaceuticals, Inc.
402-C-323

Table 14.2.1.2-1 (Page x of Y)
Surgery
Study Part 1
(Efficacy Analysis Set)

	LB 67 mg (N=XX)	LB 133 mg (N=XX)	LB 266 mg (N=XX)	Placebo (N=XX)
Duration of Surgery (min)				
n	00	00	00	00
Mean	00.0	00.0	00.0	00.0
SD	00.00	00.00	00.00	00.00
